10.1.2 Serious adverse events

An SAE is defined as any AE [appearance of (or worsening of any pre-existing)] undesirable sign(s), symptom(s) or medical conditions(s) which meets any one of the following criteria:

- is fatal or life-threatening
- results in persistent or significant disability/incapacity
- constitutes a congenital anomaly/birth defect
- requires inpatient hospitalization or prolongation of existing hospitalization, unless hospitalization is for:

- routine treatment or monitoring of the studied indication, not associated with any deterioration in condition (asthma)
- elective or pre-planned treatment for a pre-existing condition that is unrelated to the indication under study and has not worsened since signing the informed consent
- treatment on an emergency outpatient basis for an event not fulfilling any of the definitions of a SAE given above and not resulting in hospital admission
- social reasons and respite care in the absence of any deterioration in the patient's general condition
- is medically significant, e.g. defined as an event that jeopardizes the patient or may require medical or surgical intervention to prevent one of the outcomes listed above.

All new malignant neoplasms will be assessed as serious under "medically significant" if other seriousness criteria are not met.

Life-threatening in the context of a SAE refers to a reaction in which the patient was at risk of death at the time of the reaction; it does not refer to a reaction that hypothetically might have caused death if it were more severe (see Annex IV, ICH-E2D Guideline (2003)).

Medical and scientific judgment should be exercised in deciding whether other situations should be considered serious reactions, such as important medical events that might not be immediately life threatening or result in death or hospitalization but might jeopardize the patient or might require intervention to prevent one of the other outcomes listed above. Examples of such events are intensive treatment in an emergency room or at home for allergic bronchospasm, blood dyscrasias or convulsions that do not result in hospitalization or development of dependency or abuse (see Annex IV, ICH-E2D Guideline (2003)).

Any suspected transmission via a medicinal product of an infectious agent is also considered a serious adverse reaction.

All reports of intentional misuse and abuse of the product are also considered serious adverse event irrespective if a clinical event has occurred.

10.1.3 SAE reporting

To ensure patient safety, every SAE, regardless of causality, occurring after the patient has provided informed consent and until 30 days after the patient has stopped study participation (defined as time of last dose of study drug taken or last visit whichever is later) must be reported to Novartis within 24 hours of learning of its occurrence. Any SAEs experienced after the 30 day period following the last administration of study treatment should only be reported to Novartis if the investigator suspects a causal relationship to study treatment.

All follow-up information for the SAE including information on complications, progression of the initial SAE and recurrent episodes must be reported as follow-up to the original episode within 24 hours of the investigator receiving the follow-up information. An SAE occurring at a different time interval or otherwise considered completely unrelated to a previously reported one must be reported separately as a new event.

If the SAE is not previously documented in the Investigator's Brochure or Package Insert (new occurrence) and is thought to be related to the study treatment a Drug Safety and Epidemiology

Novartis	Confidential	Page 47 of 63
Clinical Trial Protocol (Version No. 01)		Protocol No. CQMF149G2203

Department associate may urgently require further information from the investigator for health authority reporting. Novartis may need to issue an Investigator Notification (IN) to inform all investigators involved in any study with the same study treatment that this SAE has been reported. Suspected Unexpected Serious Adverse Reactions (SUSARs) will be collected and reported to the competent authorities and relevant ethics committees in accordance with EU Guidance 2011/C 172/01 or as per national regulatory requirements in participating countries.

10.1.4 Pregnancy reporting

Pregnancies

Sexually active patients are excluded from the study. In the event the patient become pregnant, and to ensure patient safety, each pregnancy occurring after signing the informed consent must be reported to Novartis within 24 hours of learning of its occurrence. The pregnancy should be followed up to determine outcome, including spontaneous or voluntary termination, details of the birth, and the presence or absence of any birth defects, congenital abnormalities, or maternal and/or newborn complications.

Pregnancy must be recorded on the Pharmacovigilance Pregnancy Form and reported by the investigator to the local Novartis Drug Safety and Epidemiology Department. Pregnancy Follow-up should be recorded on the same form and should include an assessment of the possible relationship to the study treatment. Any SAE experienced during the pregnancy and unrelated to the pregnancy must be reported on a SAE form.

Pregnancy tests are required of female patients partcipating in the study who have reached menarche. For details regarding pregnancy testing please refer to Table 8-1 and Section 8.4.3.

Tracking of pregnancy cases occurs until after Expected Delivery Date (EDD) for all prospective pregnancy cases received from clinical studies

- EDD +1 month (mandatory for all cases). Requesting the pregnancy outcome and othe relinically relevant pregnancy data or changes in data
- EDD+2 month (mandatory if no answer is obtained after request at EDD+1 month). A reminder letter for the outcome
- The follow up at EDD+3 and EDD+12 months is mandatory for all cases of live birth and unknown outcome. Information on the status of the baby 3 months after delivery and information on any development issue or abnormality that would not be seen at birth must be collected

10.1.5 Reporting of study treatment errors including misuse/abuse

Medication errors are unintentional errors in the prescribing, dispensing, administration or monitoring of a medicine while under the control of a healthcare professional, patient or consumer (EMA definition).

Misuse refers to situations where the medicinal product is intentionally and inappropriately used not in accordance with the protocol.

Abuse corresponds to the persistent or sporadic, intentional excessive use of a medicinal product, which is accompanied by harmful physical or psychological effects.

Novartis	Confidential	Page 48 of 63
Clinical Trial Protocol (Version No. 01)		Protocol No. CQMF149G2203

Study treatment errors and uses outside of what is foreseen in the protocol will be recorded on the appropriate CRF irrespective of whether or not associated with an AE/SAE and reported to Safety only if associated with an SAE. Misuse or abuse will be collected and reported in the safety database irrespective of it being associated with an AE/SAE within 24 hours of Investigator's awareness.

Table 10-1	Guidance for capturing the study treatment errors including
	misuse/abuse

Treatment error type	Document in Dosing CRF (Yes/No)	Document in AE eCRF	Complete SAE form
Unintentional study treatment error	Yes	Only if associated with an AE	Only if associated with an SAE
Misuse/Abuse	Yes	Yes	Yes, even if not associated with a SAE

For more information on AE and SAE definition and reporting requirements, please see the respective sections.

10.1.6 Concept 1 related adverse event reporting

Any Concept 1 device related adverse events must be reported to Novartis within 24 hours of learning of its occurrence. Concept 1 device related adverse events must be recorded on the relevant device-related pages of the CRF. Country regulations have to be followed for the Concept 1 device related adverse events reporting to Health Authorities and/or Ethics Committees.

The investigator has the responsibility for managing the safety of individual patients.

10.2 Additional Safety Monitoring

10.2.1 Liver safety monitoring

To ensure patient safety and enhance reliability in determining the hepatotoxic potential of an investigational drug, a standardized process for identification, monitoring and evaluation of liver events has to be followed. The following two categories of abnormalities / adverse events have to be considered during the course of the study (irrespective of whether classified/reported as (S)AE):

- Liver laboratory triggers, which will require repeated assessments of the abnormal laboratory parameter
- Liver events, which will require close observation, Follow-up monitoring and completion of the standard base liver CRF pages

Please refer to Table 16-1 in Section 16.2 for complete definitions of liver laboratory triggers and liver events.

Once a participant is exposed to study treatment, every liver laboratory trigger or liver event as defined in Table 16-1 of Section 16.2 should be followed up by the investigator or designated personal at the trial site as summarized below. Detailed information is outlined in Table 16-2 in Section 16.2.

For the liver laboratory trigger:

• Repeating the liver function test (LFT) within the next week to confirm elevation.

These LFT repeats will be performed using the central laboratory. If this is not possible, then the repeats can be performed at a local laboratory to monitor the safety of the patient. If a liver event is subsequently reported, any local LFTs previously conducted that are associated with this event must be reported on the Liver CRF pages.

Confidential

If the initial elevation is confirmed, close observation of the patient will be initiated, including consideration of treatment interruption if deemed appropriate.

For the liver events:

- Discontinuation of the investigational drug (refer to the Discontinuation of study treatment, Section 9.1.1) if appropriate
- Hospitalization of the patient if appropriate
- A causality assessment of the liver event via exclusion of alternative causes (e.g., disease, co-medications)
- An investigation of the liver event which needs to be followed until resolution.

These investigations can include serology tests, imaging and pathology assessments, hepatologist's consultancy, obtaining more detailed history of symptoms and prior or concurrent diseases, history of concomitant drug use, exclusion of underlying liver disease.

All follow-up information and procedures performed must be recorded as appropriate in the CRF.

11 Data Collection and Database management

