16.2 Appendix 2: Liver event and laboratory trigger definitions & follow-up requirements

 Table 16-1
 Liver event and laboratory trigger definitions

	Definition/ threshold
Liver laboratory triggers If ALT, AST and total bilirubin normal at	• ALT or AST > 5 × ULN
	 ALP > 2 × ULN (in the absence of known bone pathology)
baseline:	 Total bilirubin > 3 × ULN (in the absence of known Gilbert syndrome)
	 ALT or AST > 3 × ULN and INR > 1.5
	 Potential Hy's Law cases (defined as ALT or AST > 3 × ULN and Total bilirubin > 2 × ULN [mainly conjugated fraction] without notable increase in ALP to > 2 × ULN)
	Any clinical event of jaundice (or equivalent term)
	 ALT or AST > 3 × ULN accompanied by (general) malaise, fatigue, abdominal pain, nausea, or vomiting, or rash with eosinophilia
	 Any adverse event potentially indicative of a liver toxicity*
If ALT or AST abnormal at baseline:	• ALT or AST > 2x baseline or > 300 U/L (whichever occurs first)

*These events cover the following: hepatic failure, fibrosis and cirrhosis, and other liver damagerelated conditions; non-infectious hepatitis; benign, malignant and unspecified liver neoplasms ULN: upper limit of normal

Table 16-2	Follow up requirements for liver laboratory triggers with liver
	symptoms

ALT	TBL	Liver Symptoms	Action			
ALT increase without b	oilirubin increase:					
If normal at baseline: ALT > 3 x ULN	Normal For patients with		 No change to study treatment 			
If elevated at baseline:	Gilbert's syndrome: No change in baseline TBL		 Measure ALT, AST, ALP, GGT, 			
ALT > 2 x baseline or > 300 U/L (whichever occurs first)		None	TBIL, INR, albumin, CK, and GLDH in 48-72 hours.			
			 Follow-up for symptoms. 			
If normal at baseline:	Normal		 Interrupt study 			
ALT > 5 x ULN for more than two weeks	For patients with Gilbert's syndrome: No		drug			
If elevated at baseline:	change in baseline TBL	None	 Measure ALT, AST, ALP, GGT, TBIL, INR, 			
ALT > 3 x baseline			albumin, CK, and			

ALT	TBL	Liver Symptoms	Action
or > 300 U/L (whichever occurs first) for more than two			GLDH in 48-72 hours.
weeks			 Follow-up for symptoms.
If normal at baseline:	Normal	None	Initiate close
ALT > 8 x ULN		NULLE	monitoring and
ALT increase with bilir	ubin increase:		workup for
If normal at baseline:	TBL > 2 x ULN (or INR		competing etiologies.
ALT > 3 x ULN	> 1.5)		 Study drug can be
If elevated at baseline:	For patients with Gilbert's syndrome:	None	restarted only if another etiology is

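### For children with normal baseline liver values, Section 10.2.1 and Table 16-1 start liver follow-up at higher ALT and bilirubin values than Tables 16-2 and 16-3, so whether two ranges need a retest is unclear

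*Protocol*

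**What the plan says.** Protocol Section 10.2.1 promises a standardized process for liver findings. On definitions it says: "Please refer to Table 16-1 in Section 16.2 for complete definitions of liver laboratory triggers and liver events". It then states that, after exposure, "every liver laboratory trigger or liver event as defined in Table 16-1 of Section 16.2 should be followed up by the investigator". For how to do so it adds: "Detailed information is outlined in Table 16-2 in Section 16.2". Section 10.2.1 does not mention Table 16-3.

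Section 16.2 holds the three tables.

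- **Table 16-1**, for ALT, AST and total bilirubin normal at baseline, lists "ALT or AST > 5 × ULN" and "Total bilirubin > 3 × ULN (in the absence of known Gilbert syndrome") as stand-alone entries. ALT or AST above 3 × ULN appears only in combination: with INR above 1.5, with bilirubin above 2 × ULN as a potential Hy's Law case, or with symptoms.
- **Table 16-2** opens with the row "If normal at baseline: ALT > 3 x ULN", with bilirubin normal and None in the symptom column. The action is no change to treatment and a repeat panel in 48 to 72 hours. The table's title, however, describes triggers accompanied by liver symptoms.
- **Table 16-3**, titled as follow-up for liver laboratory triggers, opens its isolated-bilirubin rows at more than 1.5 and up to 3.0 × ULN. The action is to maintain treatment and repeat liver tests within 48 to 72 hours.

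**The concern.** A table of follow-up requirements for triggers should begin where the trigger definitions begin. Here both follow-up tables begin lower. An investigator who starts from Section 10.2.1 and Table 16-1 can conclude that an asymptomatic ALT of 4 × ULN is not a trigger and needs no protocol-driven repeat. An investigator who opens Table 16-2 finds that the same value calls for a repeat panel within three days.

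The timing gives this some weight. Under Section 8.4.1 and Table 16-5, the only scheduled post-dose chemistry for completers is taken 6 hours after QMF149 on Day 6. Both single doses have been given by then, so instructions to maintain or interrupt treatment have little left to act on and the retest is the main action remaining. Table 8-1 schedules no further blood draw; the next planned contact is the safety call 30 days after the last dose. If a site does not retest, no later scheduled sample would show whether the value rose or settled.

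**Working it through.** No sample size, power or event count is involved and the plan gives no figure to reproduce. The check is a row-by-row comparison of thresholds.

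**Step 1. ALT, normal baseline, bilirubin normal, no symptoms, INR not above 1.5.**

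| ALT (× ULN) | Table 16-1 | Table 16-2 |
|---|---|---|
| up to 3 | not listed | no row |
| above 3, up to 5 | not listed | repeat panel in 48–72 h |
| above 5 | trigger | repeat panel in 48–72 h (the row above 3 × ULN includes it) |

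The two sources differ only in the middle row. Example: ALT of 4 × ULN.

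**Step 2. Isolated total bilirubin, normal baseline, no known Gilbert syndrome.**

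| Bilirubin (× ULN) | Table 16-1 | Table 16-3 |
|---|---|---|
| up to 1.5 | not listed | no row |
| above 1.5, up to 3.0 | not listed | repeat tests within 48–72 h |
| above 3 | trigger | rows for above 3 to 10 and above 10 |

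Again only the middle row differs. Example: bilirubin of 2 × ULN.

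**Step 3. ALT raised at baseline.** Table 16-1 uses "ALT or AST > 2x baseline or > 300 U/L (whichever occurs first"), and the first row of Table 16-2 uses the same limits for ALT. The ALT mismatch is therefore confined to normal baseline values.

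**Step 4. Which branch applies to most children?** Table 8-1 schedules chemistry before dosing only at Screening. Exclusion 14 removes children with clinically significant abnormal laboratory values at that visit. The normal-baseline branch should therefore cover most participants, although a raised value judged not clinically significant could still enter.

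**Step 5. Does another section settle it?**

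- Section 6.5.2.1 covers transaminase and bilirubin rising together, so neither isolated range falls under it.
- Section 8.4.1 asks for regular follow-up of clinically significant laboratory abnormalities. That turns on investigator judgement and sets no threshold. It also asks for bilirubin above 1.5 × ULN to be split into direct and indirect fractions, which is a further measurement and not a repeat test.
- Section 16.1 states that there are no study-specific criteria for notable laboratory values.

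None of these says whether a result in either range must be repeated.

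**The case against.** The strongest reply is that nothing here is a direct contradiction. Section 10.2.1 says that Table 16-1 findings should be followed up; it does not say that other results need no follow-up, and the same paragraph sends the reader on to Table 16-2. A site that follows all of Section 16.2 retests in both ranges and breaches nothing. This stands, and it rules out the stronger inference that Section 10.2.1 restricts follow-up to Table 16-1 or that the tables impose opposite rules. What remains is that Section 10.2.1 presents the Table 16-1 definitions as complete, does not cite Table 16-3, and relies on a Table 16-2 whose title suggests symptomatic cases. Each of these gives a site a reasonable ground for not retesting.

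Two further inferences are tempting and not supported.

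- *The number of liver triggers depends on the table read.* Trigger status is set by Table 16-1 alone; Tables 16-2 and 16-3 set actions. The SAP plans no liver-trigger count: its Section 2.8.3 lists, flags and summarises laboratory data.
- *Isolated AST or ALP triggers have no follow-up action because they have no row of their own.* Section 10.2.1 gives a general action for any liver laboratory trigger: "Repeating the liver function test (LFT) within the next week to confirm elevation". Close observation follows if the rise is confirmed.

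Section 8.4.1 is also a partial backstop. A child with a value the investigator considers clinically significant would not simply wait for the 30-day call. That reduces the risk without fixing the threshold.

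Finally, the extracted text of Table 16-1 shows a label for triggers and none for liver events, so a label may have been lost. The numerical limits are unaffected, and Section 10.2.1 ties follow-up to both categories.

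**Conclusion.** The point holds as a misalignment of thresholds. For children with normal baseline values, two ranges can reasonably be read either way: asymptomatic ALT above 3 and up to 5 × ULN with normal bilirubin, and isolated total bilirubin above 1.5 and up to 3 × ULN. The ALT part does not arise when ALT is raised at baseline.

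The effect is small. About 32 children are to be recruited for 24 completers, each drug is given once, and completers have one scheduled post-dose chemistry sample. The documents give no expected rate of liver abnormalities, so the statement that few children will be affected is an assumption drawn from these features and from Exclusion 14. That sites would in fact act differently is a possibility the wording allows. The primary comparison of MF AUC0-6h and Cmax is unaffected.

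It is still worth correcting, because it concerns safety follow-up in children at the last scheduled blood test. No view is taken on which threshold is right.

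**What to change.** Reconcile Section 10.2.1 with Tables 16-1, 16-2 and 16-3 so that each ALT and total bilirubin range has one follow-up status. Cite Table 16-3 in Section 10.2.1, state which table governs if they differ, and make the title of Table 16-2 match its rows, some of which cover patients without symptoms. The sponsor's clinical team decides the thresholds.

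The same edit could reconcile the repeat interval, which is one week in Section 10.2.1 and 48 to 72 hours in Tables 16-2 and 16-3. That is a separate matter from which results qualify.

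The cost is protocol wording only. It adds no procedure beyond what one of the tables already requires, and neither the SAP nor the sample size changes.

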6.5 Dose escalation and dose modification

Investigational or other study treatment dose adjustments and/or interruptions are not permitted.

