6.5.1 Dose modifications

Study drug dose adjustments and/or interruptions are not permitted.

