ALT > 2 x baseline	Doubling of direct bilirubin		identified and liver
or > 300 U/L	Sindon		enzymes return to
(whichever occurs first)			baseline.
If normal at baseline:			
ALT > 3 x ULN			
If elevated at baseline:	Normal or elevated	Severe fatigue, nausea, vomiting, right	
ALT > 2 x baseline		upper quadrant pain	
or > 300 U/L (whichever occurs first)			

I able 16-3 Follow up requirements for liver laboratory triggers	Table 16-3	rements for liver laboratory triggers
--	------------	---------------------------------------

Criteria	Actions required	Follow-up monitoring			
Total Biliruin (isolated)					
>1.5 – 3.0 ULN	 Maintain treatment Repeat LFTs within 48-72 hours 	Monitor LFTs weekly until resolution ^a to ≤ Grade 1 or to baseline			
> 3 - 10 × ULN (in the absence of known Gilbert syndrome)	 Interrupt treatment Repeat LFT within 48-72 hours Hospitalize if clinically appropriate Establish causality Record the AE and contributing factors (e.g. conmeds, med hx, lab) in the appropriate CRF 	Monitor LFTs weekly until resolution ^a to ≤ Grade 1 or to baseline (ALT, AST, total bilirubin, Alb, PT/INR, ALP and GGT) Test for hemolysis (e.g. reticulocytes, haptoglobin, unconjugated [indirect] bilirubin)			
> 10 x ULN	 Discontinue the study treatment immediately Hospitalize the patient Establish causality 	ALT, AST, total bilirubin, Alb, PT/INR, ALP and GGT until resolution ^a (frequency at investigator discretion)			

Criteria	Actions required	Follow-up monitoring		
	 Record the AE and contributing factors(e.g. conmeds, med hx, lab)in the appropriate CRF 			
Any AE potentially indicative of a liver toxicity*	 Consider study treatment interruption or discontinuation 	Investigator discretion		
	 Hospitalization if clinically appropriate 			
	Establish causality			
	 Record the AE and contributing factors(e.g., conmeds, med hx, lab)in the appropriate CRF 			
values at three subsequent moni	ome of one of the following: (1) ret toring visits at least 2 weeks apart) liver transplantation, and (5) deat	, (3) remain at elevated level		
	g: hepatic failure, fibrosis and cirrh ε hepatitis; benign, malignant and ι			

Based on investigator's discretion investigation(s) for contributing factors for the liver event can include: Serology tests, imaging and pathology assessments, hepatologist's consultancy; obtaining more detailed history of symptoms and prior or concurrent diseases, history of concomitant drug use, exclusion of underlying liver disease.

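### Liver rules conflict: interrupting study drug is both forbidden and listed as an action, and the same finding carries two repeat-test deadlines

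*Protocol*

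**What the plan says.** On interruption, protocol section 6.5 states "Investigational or other study treatment dose adjustments and/or interruptions are not permitted", and section 6.5.1 repeats it: "Study drug dose adjustments and/or interruptions are not permitted". Neither makes an exception for liver findings. Section 10.2.1 nevertheless describes close observation after a confirmed elevation, "including consideration of treatment interruption if deemed appropriate". Table 16-2 lists "Interrupt study" drug as an action beside the row "ALT > 5 x ULN for more than two weeks". It also allows study drug to be restarted, but only once a different cause has been found and the enzymes are back to baseline. Table 16-3 requires interruption for isolated bilirubin above 3 and up to 10 × ULN.

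On the repeat test, section 10.2.1 applies one instruction to every liver laboratory trigger in Table 16-1: "Repeating the liver function test (LFT) within the next week to confirm elevation". It calls itself a summary and refers to Table 16-2 for detail. Table 16-2 asks for a repeat panel in 48-72 hours. Table 16-3 says "Repeat LFTs within 48-72 hours" for isolated bilirubin of 1.5 to 3.0 × ULN and gives the same window for the band above 3 and up to 10 × ULN.

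Sections 6.1.4 and 6.1.5 fix treatment at one dose of each product, on Day 1 and Day 6. Table 8-1 gives the Day 6 visit a window of -0/+3 days.

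**The concern.** Section 10.2.1 sets out to provide a standardised process for liver findings. A site that follows it should reach one retest date and one decision about any remaining dose. As written, two sites with the same result could act differently and each point to the protocol. The passages also disagree on whether interruption is available at all.

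What is at stake is the handling of individual children. After the Day 6 chemistry sample, the only further scheduled contact for a completer is the telephone call 30 days after the last dose. No scheduled visit forces a retest, so the written deadline has to do that work. The interruption wording looks like text for continuous dosing, where stopping and resuming have a plain meaning. Here there is at most one dose left to withhold, and section 9.2 gives no further access to a child who has been discontinued.

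**Working it through.** The plan states no figure to reproduce. The check sets the passages side by side and compares time windows.

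**1. Do the two deadlines apply to the same finding?**

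| Finding | Trigger in Table 16-1? | Repeat under 10.2.1 | Repeat under Tables 16-2/16-3 | Dosing action in the tables |
|---|---|---|---|---|
| ALT > 5 × ULN, normal bilirubin, no symptoms | Yes | Up to 7 days | 48-72 h (meets the ALT > 3 × ULN row of Table 16-2) | No change; interrupt if it lasts more than two weeks |
| Isolated bilirubin > 3-10 × ULN, no Gilbert syndrome | Yes | Up to 7 days | 48-72 h (Table 16-3) | Interrupt |
| Isolated bilirubin > 1.5-3.0 × ULN | No | None stated | 48-72 h (Table 16-3) | Maintain |
| AST alone > 5 × ULN, or ALP alone > 2 × ULN | Yes | Up to 7 days | No row found | No row found |

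The first two rows carry two deadlines. The third shows an oddity: a bilirubin rise too small to be a trigger has a shorter deadline than 10.2.1 gives to a larger one. In the fourth row only the one-week rule applies, so nothing collides there.

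**2. How do the windows relate?** 48 h / 24 = 2 days and 72 h / 24 = 3 days. The 2-3 day window lies inside the 7-day limit, so a repeat on day 2 or 3 satisfies both passages. A repeat on days 4 to 7 satisfies 10.2.1 and breaches the tables.

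**3. Can the interruption rows operate?** Day 6 with +3 days runs from Day 6 to Day 9. The gap between doses is 6 - 1 = 5 days to 9 - 1 = 8 days. More than two weeks means more than 14 days. An elevation that arises after the first dose can last at most 8 days before the second, so the two-week row cannot be met while a dose remains.

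**4. When would a finding be made?** Section 8.4.1 schedules chemistry at screening and 6 hours after the Day 6 dose. Table 8-1 adds an Early Termination sample. For a completer, scheduled post-dose chemistry therefore comes when no drug is left to interrupt. The interruption conflict arises only if an unscheduled test or a clinical sign appears between Day 1 and Day 6. The deadline conflict can arise for any affected trigger found on Day 6 or at Early Termination.

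**5. What does section 9.1.1 add?** It requires discontinuation for laboratory abnormalities that the physician judges clinically significant, for adverse events that make continuing harmful, and for any situation that puts the child at risk. It names no liver threshold.

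**The case against.** The strongest reply is that 10.2.1 presents itself as a summary and sends the reader to Table 16-2, so the tighter window governs and a careful site will meet both. This stands in part: the two deadlines are compatible, and a reader who infers that no retest date could satisfy both would be mistaken. But a summary should not state a looser limit than its detail, and 10.2.1 does not cite Table 16-3, which holds the bilirubin rule.

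Several stronger readings are tempting and are not supported:

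- *Potential Hy's Law cases get only a one-week repeat.* Section 6.5.2.1 gives raised transaminases with raised bilirubin a full history, a liver panel, exclusion of other causes and SAE reporting. Table 16-2 also has a row for raised ALT with raised bilirubin.
- *The site has no guidance on the Day 6 dose.* Section 9.1.1 covers discontinuation, and the liver-event branch of 10.2.1 refers to it. What is missing is a stated link from each liver threshold to that decision.
- *The tables order restart.* They permit it on conditions. Likewise, 10.2.1 asks only that interruption be considered.
- *Table 16-1 fails to separate liver events from triggers.* Only the label "Liver laboratory triggers If ALT, AST and total bilirubin normal at" is visible in the text available here, but that label is itself broken across lines and a second heading may have been lost in extraction. The original has to be checked.
- *The retest will be delayed by some multiple.* Both windows are outer limits. Neither gives an expected delay, so no ratio follows.

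It is also fair that other duties soften the effect. Section 8.4.1 requires regular follow-up of significant laboratory abnormalities, section 10.1.1 requires adverse events to be followed to resolution, and Table 16-3 adds weekly tests for isolated bilirubin rises of up to 10 × ULN. The first two set no interval for the first retest.

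**Conclusion.** The inconsistency is real, and its reach is small. Interruption is ruled out without exception in 6.5 and 6.5.1, yet it is to be considered under 10.2.1 and is listed as an action in Tables 16-2 and 16-3. For ALT > 5 × ULN with normal bilirubin and no symptoms, and for isolated bilirubin > 3-10 × ULN, two repeat deadlines apply, and days 4 to 7 fall between them. Few children are likely to be affected, and usually no dose will remain. The primary PK analysis and the sample size do not depend on any of this.

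The conclusion rests on three assumptions: no liver exception to 6.5 stands elsewhere in the protocol (none was found), the action columns of Tables 16-2 and 16-3 are read as extracted, and, for the two-week row, the elevation arises after the first dose. The documents do not show which deadline or dosing action is clinically right, and this point takes no view on that.

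**What to change.** Reconcile sections 6.5, 6.5.1, 9.1.1 and 10.2.1 with Tables 16-2 and 16-3. Each liver threshold should lead to one repeat interval and one dosing consequence that can occur in a study of two single doses. The sponsor's clinical team decides which interval and which consequence apply. The restart text and the two-week row should be reviewed at the same time, since neither fits the 5-8 day dosing phase. Section 10.2.1 should cite Table 16-3 as well as Table 16-2, and the sponsor should confirm that every Table 16-1 trigger has a row in one of the action tables. The original of Table 16-1 should be checked to see that triggers and liver events are marked separately.

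The cost is protocol wording, issued as a written amendment under section 14.1. No new visits, samples or analyses are needed.
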